2 STUDY OBJECTIVES AND ENDPOINTS

OBJECTIVES	ENDPOINTS
Efficacy	
To assess the efficacy of Roflumilast (also known as ARQ-151) cream 0.15% vs vehicle administered once daily	
Primary efficacy endpoint:
 
 • Validated Investigator Global Assessment scale for Atopic Dermatitis (vIGA-AD) Success, defined as a vIGA-AD score of 'clear' (0) or 'almost clear' (1)

	STATISTICAL ANALYSIS PLAN, Version 3.0
Protocol Number: ARQ-151-311	Sponsor: Arcutis Biotherapeutics, Inc.

OBJECTIVES	ENDPOINTS
(QD) x 4 weeks to individuals 6 years of age and older with atopic dermatitis (AD).	
plus at least a 2-grade improvement from Baseline at Week 4
 
Secondary efficacy endpoints:
 
 • In subjects with a vIGA-AD score of 'Moderate' at randomization, vIGA-AD Success at Week 4 • In subjects ≥ 12 years old with baseline Worst Itch - Numeric Rating Score (WI-NRS) ≥ 4, achievement of at least a 4-point reduction on the WI-NRS at Week 4 • In subjects ≥ 12 years old with baseline WI-NRS ≥ 4, achievement of at least a 4-point reduction on the WI-NRS at Week 2 • In subjects ≥ 12 years old with baseline WI-NRS ≥ 4, achievement of at least a 4-point reduction on the WI-NRS at Week 1 • Achievement of at least a 75% reduction in the Eczema Area and Severity Index (EASI-75) at Week 4 • vIGA-AD of 'clear' or 'almost clear' at Week 4 • vIGA-AD Success at Week 2 • vIGA-AD Success at Week 1 • vIGA-AD of 'clear' or 'almost clear' at Week 2 • vIGA-AD of 'clear' or 'almost clear' at Week 1 
Exploratory efficacy endpoints:
 
 • Other continuous efficacy endpoints include change and percent change in average weekly WI-NRS and daily WI-NRS, EASI, % body surface area (BSA) affected by AD, Dermatology Life Quality Index (CDLQI/DLQI), the Dermatitis Family Impact (DFI), Scoring Atopic Dermatitis (SCORAD), and Patient-oriented Eczema Measure (POEM) at Week 1, Week 2 and Week 4. • Other categorical efficacy endpoints include EASI-50, EASI-90, EASI-100, and vIGA-AD of 'clear' at Week 4
Safety	

	STATISTICAL ANALYSIS PLAN, Version 3.0
Protocol Number: ARQ-151-311	Sponsor: Arcutis Biotherapeutics, Inc.

OBJECTIVES	ENDPOINTS

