5.4 Windowing Conventions

Visits will be analysed as scheduled. Unscheduled, early termination visits, and/or retest measurements will only be included if a scheduled measurement is not available and the early termination or unscheduled/retest measurement falls within the analysis visit windows as described in [Table 2](#), [Table 3](#), and [Table 4](#) when appropriate. Unscheduled/retest measurements will be listed.

If there is more than one assessment for a given timepoint and analysis visit when a scheduled measurement is not available, the assessment closest to the target day will be considered.

	STATISTICAL ANALYSIS PLAN, Version 3.0
Protocol Number: ARQ-151-311	Sponsor: Arcutis Biotherapeutics, Inc.

Table 2 Analysis Visit Windows for Efficacy Endpoints, Vital Signs, CDI-2, PHQ-8, PHQ-A, C-SSRS and Local Tolerability Assessment

Analysis Visit	Target Day	Lower Limit	Upper Limit
Week 1	8	2	11
Week 2	15	12	22
Week 4	29	23	43

Table 3 Analysis Visit Windows for Clinical Laboratory, Physical Examination and PK assessment

Analysis Visit	Target Day	Lower Limit	Upper Limit
Week 4	29	23	43

Table 4 Windows for the derivation of Average Weekly WI-NRS

Days for calculation of weekly average	Week (Derived)
(-7, -1)*	Baseline
(1, 7)*	Week 1
(8, 14)	Week 2
(15, 21)	Week 3
(22, 28)	Week 4

* Day 1 WI-NRS score will be used to calculate the value for week 1 only when it is collected after the application of the first study drug (randomization for randomized subjects who were never treated with study drug). If Day 1 WI-NRS score is collected prior to or concurrently with the application of the first study drug (randomization for randomized subjects who were never treated with study drug), then the Day 1 WI-NRS score will be included in baseline calculation.

Note: With the caveat described in footnote **, if more than one WI-NRS score is available on the same day, the worst score of the day will be considered in the analyses.

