from the analysis of each multiply-imputed dataset will be transformed as per Wilson-Hilferty² before being combined using PROC MIANALYZE based on Rubin's rule. Because the Wilson-Hilferty transformation is a monotone transformation, the p-value for the CMH test is the one-sided p-value from the t distribution. This p-value will be the primary p-value used to evaluate the result according to the multiple testing strategy described in Section 6.5.

- i. Should the common MH odds ratio from the analysis of at least one of the multiply-imputed datasets be not estimable, combined common MH odds ratio and associated combined common 95% CI and p-value will not be presented. Under such circumstance, conclusions will be based on the p-value obtained from a multiple imputation test of the proportion difference, where the common proportion difference using MH weights and associated common standard errors based on the Sato variance estimator obtained from the analysis of each multiply-imputed dataset will be combined using PROC MIANALYZE based on Rubin's rule.

Similar multiple imputation method will be used for the average weekly WI-NRS and EASI total score.

For the average weekly WI-NRS (refer to Section 5.5), it's the missing average weekly WI-NRS data (i.e., those that cannot be computed because only 3 or less non-missing assessments are available during a given week) at Weeks 1, 2, 3, and 4 that will be multiply imputed, not the missing daily WI-NRS data. Since the missing average weekly WI-NRS values have a precision of 1 decimal place, the MCMC imputation for the non-monotone missing data will be restricted to values between 0 and 10, rounded to the 1st decimal (i.e., 0.1). Imputation of missing data for WI-NRS will be based on the ITT population, i.e., all randomized subjects will be included in the imputation process.

For the EASI total score (refer to Section 5.5), it's the missing EASI total score data at Weeks 1, 2, and 4 that will be imputed, not the missing EASI question score data. Since the missing EASI total scores have a precision of 1 decimal place, the MCMC imputation for the non-monotone missing data will be restricted to values between 0 and 72, rounded to the 1st decimal (i.e., 0.1). Imputation of missing data for EASI total score will be based on the ITT population.

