12 EFFICACY ANALYSIS

12.1 Primary Efficacy Endpoint Analysis

12.1.1 Primary Efficacy Endpoint and Estimand

The vIGA-AD is a static evaluation of qualitative overall AD severity. This global assessment scale is an ordinal scale with five severity grades (reported only in integers of 0 to 4). Each grade is defined by a distinct and clinically relevant morphologic description that minimizes inter-observer variability. vIGA-AD is evaluated for the entire body except the scalp, palms, and soles.

The primary efficacy endpoint is vIGA-AD success, defined as an vIGA-AD score of ‘clear’ (0) or ‘almost clear’ (1) plus at least a 2-grade improvement from Baseline at Week 4.

The primary estimand is described by the following attributes:

Population: Patients with Atopic Dermatitis

Endpoint: vIGA-AD success at Week 4

Intercurrent events: In the course of the 4-week randomized treatment period, subjects may be exposed to possible known or unknown intercurrent events that could possibly impact the estimates of the estimand, such as treatment discontinuation due to a specific adverse effect or perhaps a lack of effect. A composite strategy will be implemented that handles subjects who discontinue due to lack of efficacy or adverse event as missing not at random differently than all other subjects. That is, subjects who discontinue due to lack of efficacy or adverse event will be treated as non-responders for all pre-specified analysis visits (refer to Section 5.4) for which the subject’s last dose day falls within the analysis window or is prior to the start of the analysis window (refer to

	STATISTICAL ANALYSIS PLAN, Version 3.0
Protocol Number: ARQ-151-311	Sponsor: Arcutis Biotherapeutics, Inc.

Section 5.5) while the “Treatment Policy Strategy” will be adopted for handling intercurrent events in this study other than discontinuation due to lack of efficacy or adverse event.

Population-level summary: ratio of the odds of achieving vIGA-AD success after 4 weeks of using roflumilast cream 0.15%, relative to the odds of success after 4 weeks using a matching vehicle cream in the ITT population.

The supportive population-level summary: the proportion difference between Roflumilast cream 0.15% and vehicle groups will be provided for the patients who achieve vIGA-AD success at week 4 in the ITT population.

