For each categorical exploratory efficacy endpoint, count and percentages of subjects meeting the criteria for an exploratory efficacy endpoint will be presented by visit and treatment group based on observed data in the ITT population along with a 95% Wilson CI. Additionally, count and percentage of subjects meeting the criteria for vIGA-AD of Clear (0), EASI-50, EASI-90, and EASI-100 at Week 1 and Week 2 will also be presented by visit and treatment group based on observed data in the ITT population along with a 95% Wilson CI.

Continuous exploratory efficacy endpoints will be analyzed at Week 1, Week 2, and Week 4 and for daily WI-NRS assessments using an analysis of covariance (ANCOVA) with the factors of treatment, two stratification variables (pooled study site and randomized vIGA-AD score), and baseline of the variable under analysis as covariate. Statistical comparisons between the treatment groups will be obtained using contrasts. The Least Square (LS) mean and its standard error, difference in LS means between treatment group (i.e., active - vehicle), its standard error and associated 95% confidence interval, and p-value for difference from vehicle will be presented at each visit. These analyses will be performed based on observed data in the ITT population.

Categorical exploratory efficacy endpoints at Weeks 1, 2, and 4 will be analyzed using a CMH test adjusted for the two stratification variables (pooled study site and randomized vIGA-AD score). Common MH odds ratio, common MH proportion difference and their common associated 95% CI, adjusted for the randomization factors, will be provided. The p-value will be from a CMH test for the common MH odds ratio, unless the common MH odds ratio is not estimable. In such circumstances, the p-value will be from a MH test for the common MH proportion difference.

The analysis of these endpoints will be performed on the observed data with no imputation. The p-values will be nominal as no formal inferential testing will be done on exploratory efficacy endpoints.

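### Continuous exploratory endpoints: the observed-case ANCOVA at Week 4 can be biased if response-related dropout differs between arms, and an MMRM on the same data would assume less

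*SAP*

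**What the plan says.** SAP section 2 lists the endpoints concerned: "Other continuous efficacy endpoints include change and percent change in average weekly WI-NRS and daily WI-NRS, EASI", followed by %BSA, CDLQI/DLQI, DFI, SCORAD and POEM. Section 12.3 analyses them visit by visit "using an analysis of covariance (ANCOVA) with the factors of treatment, two stratification variables (pooled study site and randomized vIGA-AD score), and baseline" of the same variable. No post-baseline score enters the model. On missing data the section states "These analyses will be performed based on observed data in the ITT population" and, for the exploratory endpoints, "The analysis of these endpoints will be performed on the observed data with no imputation". On inferential status it states "The p-values will be nominal as no formal inferential testing will be done on exploratory efficacy endpoints". Section 12.3 plans no repeated-measures model and no missing-data sensitivity analysis.

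Section 5.4 decides who has a Week 4 value. "Unscheduled, early termination visits, and/or retest measurements will only be included if a scheduled measurement is not available", and then only if the measurement falls in the visit window, which for Week 4 is Days 23 to 43. Average weekly WI-NRS at Week 4 uses Days 22 to 28, and section 5.5 requires at least 4 daily scores.

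The responder endpoints on two of these scales are handled differently. Section 6.2.1 imputes missing EASI totals and weekly WI-NRS averages from a model that includes earlier visits; for EASI, "Imputation of missing data for EASI total score will be based on the ITT population". Under section 12.1.1, "subjects who discontinue due to lack of efficacy or adverse event will be treated as non-responders for all pre-specified analysis visits" that the last dose day falls in or precedes, and section 5.5 applies the same rule to EASI-75 and the WI-NRS reduction. No such rule is stated for the continuous scores.

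**The concern.** A subject who attends Weeks 1 and 2, responds poorly and leaves before Day 23 is absent from the Week 4 ANCOVA, and the two scores that show the poor response are not used. The Week 4 comparison is then between those who stayed. It is valid only if missingness is unrelated to the Week 4 score given arm, baseline and the stratification factors.

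The SAP names discontinuation for adverse event or lack of efficacy as an expected intercurrent event, so response-related exit is plausible. For the primary and secondary endpoints, observed-case analysis is only a sensitivity analysis. In section 12.3 it is the sole analysis. At stake are the Week 4 LS means, confidence intervals and nominal p-values for extent of disease, symptoms, itch and quality of life, which readers will take as effect estimates.

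**Working it through.** **Nothing to reproduce.** The documents give no dropout rate, SD, effect size, visit correlation or power for any continuous score. The planned power concerns vIGA-AD success and does not bear on this point.

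**Inputs from the documents.** N = 650 at 2:1, so 650 × 2/3 ≈ 433 active and 650/3 ≈ 217 vehicle; visits at Weeks 1, 2 and 4; the section 12.3 model.

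**Assumed inputs.** SD 1; lower scores better; effects at Weeks 1, 2 and 4 of -0.20, -0.35 and -0.45 SD; correlation 0.6 from baseline to Week 1 and 0.75 between adjacent later visits; monotone dropout at nominal 5%, 10% and 20%. Site and vIGA-AD strata were left out. There were 3,000 simulated trials per scenario.

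**Why the comparison between arms decides the matter.** Within one arm, let d be the fraction missing at Week 4, D the mean Week 2 score of dropouts minus that of the whole arm, and β the slope of Week 4 on Week 2. In this simplified form the observed Week 4 mean shifts by -β × D × d/(1 - d). The bias of the treatment difference is the active shift minus the vehicle shift. It cancels if d and D are the same in both arms, and it can have either sign if they are not.

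**Estimators.**
- Observed case: the treatment coefficient from regressing Week 4 on treatment and baseline, in those observed.
- Repeated measures (the likelihood estimate with unstructured covariance under monotone dropout): τ1 from Week 1 on treatment and baseline; τ2 = b2(trt) + b2(Y1) × τ1; τ4 = b4(trt) + b4(Y1) × τ1 + b4(Y2) × τ2.

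**Results at Week 4** (the percentage is the understatement relative to full data):

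| Nominal dropout; mechanism | Realised dropout, active/vehicle | Full data | Observed case | Repeated measures |
|---|---|---|---|---|
| 5%; same in both arms | 4.3%/5.5% | -0.452 | -0.447 (1.1%) | -0.452 |
| 5%; poor response, vehicle only | 5.2%/5.5% | -0.450 | -0.426 (5.4%) | -0.450 |
| 10%; completely at random | 10.1%/10.1% | -0.450 | -0.450 (0%) | -0.450 |
| 10%; same in both arms | 8.1%/10.2% | -0.449 | -0.440 (2.0%) | -0.450 |
| 10%; poor response, vehicle only | 10.1%/10.1% | -0.449 | -0.406 (9.6%) | -0.449 |
| 10%; opposite mechanisms | 23.8%/10.2% | -0.451 | -0.298 (33.9%) | -0.450 |
| 10%; depends on unseen Week 4 score | 5.7%/8.5% | -0.451 | -0.429 (4.8%) | -0.437 (3.1%) |
| 20%; same in both arms | 15.8%/19.4% | -0.449 | -0.432 (3.8%) | -0.448 |
| 20%; poor response, vehicle only | 20.6%/19.3% | -0.450 | -0.368 (18.2%) | -0.449 |

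Dropout that depended only on baseline gave no bias in either model. With no true effect at the nominal 10% setting, the same mechanism in both arms gave no bias, and vehicle-only response-driven dropout gave +0.043 SD. With no effect the arms are exchangeable, so active-only response-driven dropout would give about the same size with the sign reversed, in favour of active. With skewed (lognormal) scores at 10%, observed-case understatement was 6.7% to 33.1%, and the repeated-measures model left 0.7% to 2.5%.

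**Second set of assumptions** (effect 0.40 SD, post-baseline correlations 0.60 to 0.75, dropout after Week 2). Equal 8% dropout under one mechanism gave no bias. At 6% active and 12% vehicle, one shared mechanism gave 0.372, and 0.372/0.40 = 0.93 (7% low). With only vehicle dropout following poor response, the same rates gave 0.341 (15% low). The repeated-measures estimate was 0.397 to 0.402 in every case.

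**Would the section 6.2.1 datasets serve instead?** For adverse-event and lack-of-efficacy discontinuations, section 6.2.1 deletes the efficacy data of any visit whose window contains the last dose day or starts after it. The Week 2 window is Days 12 to 22, so a last dose on one of those days removes the Week 2 score before imputation. Simulated at 6% and 12%, with vehicle-only response-driven dropout recorded as lack of efficacy: full data 0.402, observed case 0.346, MMRM 0.402, ANCOVA on the imputed datasets 0.371. The share of bias left is (0.402 - 0.371)/(0.402 - 0.346) = 0.031/0.056 = 55%; another run left about 40%.

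**The case against.** The strongest objection is that little hangs on this. The endpoints are exploratory with nominal p-values, and EASI and WI-NRS already have multiple-imputation, non-responder and observed-case analyses as secondary responder endpoints. That stands, and it limits the point to a cheap improvement.

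Second, the larger figures come from chosen mechanisms. The 34% case needs opposite mechanisms in the two arms and about 24% dropout on active. With one mechanism in both arms the loss was 1% to 4% in the first set and 0% to 7% in the second. That also stands. A reader might infer that response-dependent dropout alone biases the estimate, but the equal-dropout case shows no bias.

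Third, some early-termination values are already used at Week 4, namely those in Days 23 to 43. True, but this does not help a subject last seen before Day 23.

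Fourth, an MMRM does not bring these results into line with the responder endpoints. It assumes MAR for the very subjects whom section 12.1.1 counts as non-responders, and so targets a hypothetical-type effect for them. That stands. It is a reason to state the estimand, but not a reason to keep a model that assumes more about missingness.

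**Conclusion.** The point holds as a cheap improvement. The Week 4 observed-case ANCOVA leaves out the Week 1 and Week 2 scores of subjects without a Week 4 value. It can be biased when dropout depends on post-baseline response and its rate or mechanism differs between arms. When both are alike, the bias is near zero. The actual size cannot be derived from the documents. The simulated figures illustrate assumed dropout, effects and correlations and do not predict this trial.

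Three stronger readings are not supported. One is that the trial's efficacy conclusions are at risk: primary and secondary endpoints use other methods and are unaffected. Another is that the bias has a known direction: the scenarios run understate the effect, but the mirror pattern would overstate it. The third is that an MMRM removes all bias: it does so under MAR with a correctly specified model, only reduces it when dropout depends on the unseen score, and leaves a small remainder with skewed scores. Subjects with no post-baseline score inform neither model.

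**What to change.** In SAP section 12.3, for EASI, %BSA, SCORAD, POEM, DLQI/CDLQI, DFI and average weekly WI-NRS, make the main analysis of change and of percent change one MMRM per scale. Include treatment, visit, treatment-by-visit, baseline, baseline-by-visit, pooled site and randomized vIGA-AD, with unstructured covariance. Report the treatment contrast at each visit. Keep the observed-case ANCOVA as a sensitivity analysis.

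State the estimand: the model assumes MAR and targets a hypothetical-type effect for adverse-event and lack-of-efficacy discontinuations, unlike the composite strategy in section 12.1.1.

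Leave daily WI-NRS as observed-case, because an unstructured model over about 28 daily scores is impractical. Do not substitute ANCOVA on the section 6.2.1 datasets, since they drop the last scores of the subjects who matter most here.

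The cost is a paragraph of SAP text and routine programming, with no new data. Made before unblinding, the change is pre-specified; made later, it would be post hoc.

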12.4 Subgroup Analysis

With the following exception, analyses of the primary and secondary efficacy endpoints (refer to Sections 12.1 and 12.2, respectively) will be repeated by subgroups (refer to Section 6.6) based on the multiple imputation data using mITT, ITT or WI-NRS population, as applicable (refer to Section 12.2). The exception is that the subgroup analyses by randomized vIGA-AD score and by actual baseline vIGA-AD score will not be performed for the secondary efficacy endpoint of vIGA-AD Success based on the vIGA-AD Moderate ITT population.

The following alternatives could be implemented if the odds ratio and/or proportion difference are not estimable:

	STATISTICAL ANALYSIS PLAN, Version 3.0
Protocol Number: ARQ-151-311	Sponsor: Arcutis Biotherapeutics, Inc.

1. An unstratified model can be used if odds ratios are not estimable due to over-stratification, i.e., too few events for the number of strata.
2. If the between-imputation variance of odds ratios and/or proportion difference is 0, i.e., the estimates are equal across all imputations, the estimates from any imputation will be reported.

Should a specific subgroup have less than 10 subjects across both treatment groups, no statistical inference will be performed. Forest plots of subgroup analysis for primary efficacy endpoint and secondary efficacy endpoints will also be provided.

No subgroup analyses will be presented for the exploratory efficacy endpoint (refer to Section 2).

12.5 Summary of Primary and Secondary Efficacy Analysis

Table 5 provides a summary of the primary and sensitivity analyses that will be provided for primary and secondary efficacy endpoints.

Table 6 Summary of Primary and Secondary Efficacy Analyses

Efficacy Endpoint	Primary Analysis	Sensitivity Analysis
Primary (refer to Section 12.1)		
vIGA-AD Success (a score of '0' or '1' plus at least a 2-grade improvement) at week 4	ITT, multiple imputation (CMH)	#1 mITT, multiple imputation (CMH) #2 ITT, Tipping point (CMH)) #3 ITT, non-responder imputation (CMH) #4 ITT, observed data (CMH) #5 PP, observed data (CMH) #6 ITT, multiple imputation (CMH) and a different site pooling strategy (CMH) #7 ITT, multiple imputation (CMH) by pooled study site #8 ITT, multiple imputation (CMH) and removing one pooled study site at the time
Secondary (refer to Section 12.2)		

	STATISTICAL ANALYSIS PLAN, Version 3.0
Protocol Number: ARQ-151-311	Sponsor: Arcutis Biotherapeutics, Inc.

vIGA-AD Success (a score of '0' or '1' plus at least a 2-grade improvement) at week 4	vIGA-AD Moderate ITT, multiple imputation (CMH)	#1 vIGA-AD Moderate ITT, Tipping point (CMH) #2 vIGA-AD Moderate ITT, non-responder imputation (CMH) #3 vIGA-AD Moderate ITT, observed data (CMH) #4 vIGA-AD Moderate PP, observed data (CMH)
Family 1 ($\alpha=0.03$): Average weekly WI-NRS Success (achievement of at least a 4-point reduction) at weeks 1,2, and 4	WI-NRS population, multiple imputation (CMH)	#1 WI-NRS, non-responder imputation (CMH) #2 WI-NRS, observed data (CMH)
Family 2 ($\alpha=0.02$ or $\alpha=0.05$): EASI-75 at week 4	ITT, multiple imputation (CMH)	#1 ITT, non-responder imputation (CMH) #2 ITT, observed data (CMH)
Family 2 ($\alpha=0.02$ or $\alpha=0.05$): vIGA-AD Success (a score of '0' or '1' plus at least a 2-grade improvement) at weeks 1 and 2	ITT, multiple imputation (CMH)	#1 ITT, non-responder imputation (CMH) #2 ITT, observed data (CMH)
Family 2 ($\alpha=0.02$ or $\alpha=0.05$): vIGA-AD score of '0' or '1' at weeks 1, 2 and 4	ITT, multiple imputation (CMH)	#1 ITT, non-responder imputation (CMH) #2 ITT, observed data (CMH)

